**8.2.2.2. Multiple-Organ Failure**

The analyses for MOF are summarized in Table 19. All endpoints should be presented in the same table.

**Table 19. Summary of Analyses for Multiple-Organ Failure**

Endpoint	Population	Statistical Method	Model/ Covariates/ Strata	Missing Data	Interpretation/ Comments
Organ systems that failed	Safety	Fisher exact	Vaccination group	N/A	
Meet criteria for MOF	Safety	Fisher exact	Vaccination group	N/A	
MOF associated with infection (PDI or non-PDI)	Safety	Fisher exact	Vaccination group	N/A	
MOF not associated with infection (other or unknown)	Safety	Fisher exact	Vaccination group	N/A	
Given MOF associated with PDI, confirmed Staphylococcus aureus , confirmed non- S aureus , not microbiologically confirmed	Safety	Fisher exact	Vaccination group	N/A	
MOF associated with non-PDI, confirmed S aureus , confirmed non- S aureus , not microbiologically confirmed	Safety	Fisher exact	Vaccination group	N/A	

Abbreviations: MOF = multiple-organ failure; N/A = not applicable; PDI = protocol-defined infection.

**8.2.2.3. Local Reactions and Systemic Events**

A listing will be created for local reactions and systemic events (including fever) still present on the last day that the subject’s e-diary was completed. This will not include subjects with both redness and swelling <5 caliper units on the last day. The number of days since vaccination will be computed as the stop date minus the date of vaccination, plus 1. If the event is still ongoing, then the stop date will be set to missing, as will the number of elapsed days. The listing will include site, subject, injection site (for local reactions only), vaccine group, name of local reaction or systemic event, vaccination date, stop date, ongoing (yes/no), and number of elapsed days. The listing will be sorted by vaccine group, site, subject, and name of local reaction or systemic event. The listing will include the date when the reaction resolves, or ends as “ongoing.”

Subjects reporting any severe local reaction and any severe systemic event on the same day will be identified. Their 10-day local reactions and systemic events will be listed, as well as resolution of events persisting beyond 10 days.

The proportions of subjects completing the e-diary each day will be compiled, as well as the categories “Days 1-4,” “Days 1-7,” and “All days (Days 1-10).” Subjects who fail to complete the e-diary only because of early surgery, ie, surgery on the 10th day after vaccination or earlier, will still be considered to have completed the e-diary as of the day before surgery.

For example, a subject who completes the e-diary on every day up to the 8th day, and then has surgery on the 9th day, will be considered to have completed “All days (Days 1-10).”

The proportions of subjects with at least 1 e-diary entry on or after the day of surgery will be compiled by vaccine group. Entries in e-diaries on or after the day of surgery will be excluded from analysis. These proportions will quantify what proportion of subjects may have additional local or systemic entries that were not included in the analysis.

Per protocol Section 4.1, the e-diary need not be completed on the day of surgery. The proportions of subjects with surgery on Days 1, 2, 3, etc, will be compiled to explain incomplete e-diaries.

All analyses will be performed in the safety population. No subgroup analyses are proposed.

Analyses for local reactions and systemic events are summarized in Table 20.

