7.2.1. Local Reactions and Systemic Events

7.2.1.1. Electronic Diary

The subject will be issued an e-diary, based on a personal digital assistant (PDA) or equivalent technology. Prior to vaccination, a baseline assessment (fatigue, headache, muscle pain, or joint pain over the previous month) will be recorded in the e-diary. Starting on the day of vaccination, the subject will monitor and record local reactions, systemic events, and any antipyretics or pain medication used to treat symptoms, for 10 days.* The e-diary allows recording of these assessments only within a fixed time window, thus providing the accurate representation of the subject's experience at that time. Data on local reactions, systemic events, and antipyretics/pain medication used to treat symptoms reported in the e-diary will be transferred electronically to the e-diary vendor, where they will be available for review by investigators via an Internet-based portal. At intervals agreed to by the vendor and Pfizer, the data will be transferred electronically into Pfizer's event database for analysis and reporting.

Investigators (or appropriately qualified designee) are required to review the daily e-diary data online at frequent intervals during active vaccination periods, as part of the ongoing safety review.

The investigator or designee will obtain from the subject stop dates for any symptoms ongoing on the last day that the e-diary was completed. The stop dates will be documented in the source documents and the information entered in the CRF.

*In the event that surgery occurs on the 10th day after vaccination, the e-diary data for Day 10 does not need to be completed.

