**6.2.3. Local Reactions and Systemic Events**

Day 1 is defined in this study as the day of the index surgery. References to “Days 1-10” in this section refer to the 10 days following vaccination.

The grading scales for local reactions and systemic events are derived from the Food and Drug Administration (FDA) Center for Biologics Evaluation and Research (CBER) guidelines on toxicity grading scales for healthy adult volunteers enrolled in preventive vaccine clinical trials.

Subjects will assess redness, swelling, and pain at the site of vaccination and record the symptoms in the electronic diary (e-diary) for 10 consecutive days starting on the day of vaccination. Redness and swelling will be measured and recorded in caliper units (range: 1 to 21+), and then categorized as mild, moderate, or severe based on the grading scale in Table 2.

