**Table 2. Local Reaction Grading Scale**

	GRADE 1 Mild	GRADE 2 Moderate	GRADE 3a Severe	GRADE 4b
Redness	5 to 10 caliper units (or measuring device units) 2.5 to 5.0 cm	11 to 20 caliper units (or measuring device units) 5.5 to 10.0 cm	≥21 caliper units (or measuring device units) ≥10.5 cm	Necrosis or exfoliative dermatitis b
Swelling	5 to 10 caliper units (or measuring device units) 2.5 to 5.0 cm	11 to 20 caliper units (or measuring device units) 5.5 to 10.0 cm	≥21 caliper units (or measuring device units) ≥10.5 cm	Necrosis b
Pain at injection site	Does not interfere with activity	Interferes with activity	Prevents daily activity	Emergency room visit or hospitalization

a. Subjects experiencing local reactions ≥21 caliper units (≥10.5 cm) will telephone the study site. In the event that the subject does not call, the investigator will call the subject.

b. Grade 4 assessment should be made by the investigator and recorded as an AE on the case report form.

Note: If the size of the redness and/or swelling falls between 2 caliper units, the higher caliper unit number will be recorded in the electronic diary (e-diary).

Numeric scores for the local reactions will be: none = 0, mild = 1, moderate = 2, and severe = 3.

Grade 4 will not be collected in the e-diary. Only an investigator is able to classify a subject’s local reaction as Grade 4, after physical examination of the subject or telephone contact with the subject. Any such local reactions will be recorded as AE on the CRF. In addition to their inclusion in the general AE analysis, these events will be listed and discussed separately as reactogenicity events.

The derived local reaction variables are:

1. Maximum grade during Days 1-10 after vaccination, for each local reaction.

2. Mild, moderate, or severe response during Days 1-10 after vaccination, for each local reaction.
3. Duration in days, but not for “any local reaction.”
4. Onset of the indicated local reaction in days.
5. Onset of “any local reaction” in days.

The mild, moderate, or severe response during Days 1-10 after vaccination is “yes” if present on at least 1 day.

A given local reaction is “yes” for Days 1-10 after vaccination if present on at least 1 day, is “no” if the subject reports any combination of “no” and “missing” on each of Days 1-10 after vaccination, and is “missing” if every day is missing.

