**Table 20. Summary of Analyses for Local Reactions and Systemic Events**

Endpoint	Population	Statistical Method	Model/ Covariates/ Strata	Missing Data	Interpretation/ Comments
Proportion of maximum mild, moderate, severe, and any systemic event over Days 1-10 after vaccination (fever, vomiting, diarrhea, fatigue, headache, muscle pain, joint pain, plus any systemic event); also antipyretic/pain medication use	Safety	Fisher exact	Vaccine group	See Section 6.2.3	Assess reactogenicity
Proportions of subjects with the indicated systemic event each day, plus any systemic event	Safety	Descriptive only	Vaccine group	N/A	No statistical test
Proportions of subjects with moderate or severe indicated systemic event on each day	Safety	Descriptive only	Vaccine group	N/A	No statistical test
Duration of systemic event/fever, but not for any systemic event	Safety	Mann-Whitney	Vaccine group	N/A	Assess reactogenicity
Onset of systemic event/any systemic event/fever	Safety	Mann-Whitney	Vaccine group	N/A	Assess reactogenicity
Subjects reporting any severe local reaction and any severe systemic event on the same day	Safety	N/A	Vaccine group	N/A	Listing of Days 1-10, including day of interest
Listing of unresolved reactions still present on the last e-diary day	Safety	N/A	Vaccine group	N/A	
Completing the e-diary each day	Safety	N/A	Vaccine group	N/A	
Completing the e-diary on Days 1-10	Safety	N/A	Vaccine group	N/A	Categories for days completed are 100%, 75%-<100%, 50%-74%, 25%-49%, and <25%
One or more e-diary entries on or after the day of surgery	Safety	N/A	Vaccine group	N/A	
Proportion of subjects with surgery on Days 1, 2, 3, etc, after vaccination	Safety	N/A	Vaccine group	N/A	Days with zero proportions may be omitted; eg, there is no expectation of subjects' receiving surgery on the day

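### The exclusion from the unresolved-reactions listing is worded by subject rather than by event, so ongoing pain, fever or other systemic events are dropped when redness and swelling are both under 5 caliper units

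*SAP*

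**What the plan says.** SAP 8.2.2.3 opens with the scope: "A listing will be created for local reactions and systemic events (including fever) still present on the last day" that the e-diary was completed. The next sentence restricts it: "This will not include subjects with both redness and swelling <5 caliper units on the last day". The section then names the fields to be shown, among them "injection site (for local reactions only), vaccine group, name of local reaction or systemic event", together with the vaccination date, the stop date, an ongoing flag and the number of elapsed days.

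Table 20 of the SAP carries the same output as "Listing of unresolved reactions still present on the last e-diary day", in the safety population, with no size limit and no exclusion of subjects.

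The meaning of 5 units comes from SAP Table 2, where Grade 1 redness or swelling is "5 to 10 caliper units (or measuring device units) 2.5 to 5.0 cm". Pain is also a local reaction (SAP 6.2.3: "Subjects will assess redness, swelling, and pain at the site of vaccination"), but it is graded by interference with activity and has no caliper value. Systemic events and temperature have their own scales in SAP Tables 3 and 4.

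On the data side, Protocol 7.2.1.1 asks sites for the end date of anything ongoing: "The investigator or designee will obtain from the subject stop dates for any symptoms ongoing on the last day that the e-diary was completed".

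**The concern.** The listing is meant to show, subject by subject, which events outlasted the diary and how they ended. As worded, entry depends on redness or swelling of at least 5 units on the last day. A subject who still has fever, injection-site pain, headache or joint pain, and whose redness and swelling are both below that size, does not appear. The caliper threshold has no bearing on those other events.

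Local reactions and systemic events are primary safety endpoints (Protocol 2.2.1). A programmer who follows the sentence exactly would produce a listing that does not match its own description, and nothing elsewhere in the SAP corrects it. At stake is whether this one safety listing is complete. No test or efficacy result depends on it.

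**Working it through.** The plan states no figure to reproduce, so the check is logical.

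**Step 1: apply the rule to each pattern of ongoing events.** On the last diary day let (a) be redness or swelling of at least 5 units, (b) injection-site pain, and (c) any systemic event or fever. Three yes/no conditions give 2³ − 1 = 7 patterns with something ongoing. Here a reading of no redness or no swelling is treated as below 5 units.

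| Ongoing on last day | Both redness and swelling <5? | Listed as written? |
|---|---|---|
| a | no | yes |
| a, b | no | yes |
| a, c | no | yes |
| a, b, c | no | yes |
| b | yes | **no** |
| c | yes | **no** |
| b, c | yes | **no** |

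The patterns with (a) number 2² = 4 and are kept with all their entries. The patterns without (a) number 2² − 1 = 3 and are lost. If the threshold is applied only to redness and swelling entries, all 7 stay, and only redness or swelling below 5 units goes unlisted.

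**Step 2: absent readings.** SAP 6.2.3 gives the recorded caliper range as starting at 1 and does not say how no redness, or a missing reading, compares with the limit of 5. If absence counts as having no caliper value, fewer subjects are dropped. Those with 1 to 4 units on both signs would still lose their pain, fever and systemic entries, while subjects with no redness or swelling at all would keep theirs.

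**Step 3: set the rule beside the rest of the section.** The scope sentence includes systemic events and fever. The injection-site field is reserved for local reactions, which makes sense only if systemic events also have entries. The Table 20 row has no size condition. All three disagree with an exclusion of subjects based on redness and swelling. All three agree with an exclusion of ungraded redness and swelling entries.

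**Step 4: see what other outputs retain.**
- Table 20 gives the proportion of subjects with each local reaction and each systemic event on each day, and repeats this for moderate or severe events. SAP 6.2.3 adds the daily proportion with fever.
- Duration is compared between groups for pain, redness, swelling, systemic events and fever. If an event is unresolved at the last diary date, the resolution date on the case report form is used (SAP 6.2.3), and systemic events follow the same derivation.
- If that resolution date is missing, duration is set to missing. Such an event leaves the duration analysis, and the ongoing flag in this listing is where it would be shown as unresolved.
- The second listing in 8.2.2.3 includes resolution after Day 10, but only for subjects with a severe local reaction and a severe systemic event on the same day. It covers little of the gap.

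**The case against.** The strongest reply is that this is a drafting slip with an obvious intent. The scope, the fields, Table 20 and the Grade 1 limit all suggest that the author wanted to keep ungraded redness and swelling from being listed as unresolved, and a sensible programmer might do that without being told. The intent is probably as described, but the SAP does not state it. A specification that has to be overridden to give the right output needs correcting. One could also note that the Table 20 row speaks only of reactions. Even if that meant local reactions alone, ongoing pain would still be wrongly dropped.

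The second reply is that persistence is reported elsewhere, and this largely stands. A reader might infer that the study report would suggest that almost nothing but large redness or swelling outlasts the diary, or that this listing is the only planned evidence on persistence. The documents do not support either inference. Daily proportions show pain, fever and systemic events by group up to Day 10, and the duration analyses bring in resolution after the diary, neither with a caliper condition. Grade 4 events are also listed and discussed separately (SAP 6.2.3). What remains is the subject-level display, including events with no recorded resolution date.

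**Conclusion.** The exclusion sentence is wrong as written. It removes whole subjects on redness and swelling size from a listing that is also meant to show ongoing pain, fever and other systemic events. The conclusion rests on the literal wording and on treating absent redness or swelling as below 5 units. Under the alternative treatment in Step 2 it still holds, for fewer subjects.

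The point is minor. It concerns one descriptive listing. Stop dates are still collected, and subjects with redness or swelling of 5 units or more keep all their entries. Daily proportions and duration analyses are unaffected by the sentence. Its main practical consequence is for events with a missing resolution date: they drop out of the duration analysis and, outside the narrow listing of same-day severe events and the separate handling of Grade 4 events, would be shown as ongoing only here.

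A reader might also want to say that the rule omits nearly all subjects with another ongoing event. The documents give no rates of ongoing pain, fever, systemic events, redness or swelling at diary end, so any percentage would only restate an assumption. The number affected cannot be computed.

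**What to change.** Replace the exclusion sentence in SAP 8.2.2.3 with one that acts on the event, for example: *Redness or swelling measuring <5 caliper units on the last day (or absent) will not be listed as an ongoing reaction; all other ongoing local reactions, fever and systemic events will be listed regardless of redness and swelling size.* Add how a missing redness or swelling reading on the last day is handled.

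The Table 20 row can stay as it is. The cost is this wording change and a small edit to the listing program. No data collection changes, because sites already obtain stop dates for any ongoing symptom.

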**Table 20. Summary of Analyses for Local Reactions and Systemic Events**

Endpoint	Population	Statistical Method	Model/ Covariates/ Strata	Missing Data	Interpretation/ Comments
Proportions of maximum mild, moderate, severe, and any reaction over Days 1-10 after vaccination (redness, swelling, pain, plus any local reaction)	Safety	Fisher exact	Vaccine group	See Section 6.2.3	Assess reactogenicity
Proportions of subjects with the indicated reaction (redness, swelling, pain, plus any local reaction) on each day	Safety	Descriptive only	Vaccine group	N/A	No statistical test
Proportions of subjects with moderate or severe indicated reaction (redness, swelling, pain, plus any local reaction) on each day	Safety	Descriptive only	Vaccine group	N/A	No statistical test
Duration of local reaction in days, but only for pain, swelling, and redness	Safety	Mann-Whitney	Vaccine group	N/A	Assess reactogenicity
Onset day of local reaction for pain, swelling, redness, and any local reaction	Safety	Mann-Whitney	Vaccine group	N/A	Assess reactogenicity
Baseline assessment of fatigue, headache, muscle pain, and joint pain over the previous month	Safety	Fisher exact	Vaccine group	N/A	Assess reactogenicity

**Table 20. Summary of Analyses for Local Reactions and Systemic Events**

Endpoint	Population	Statistical Method	Model/ Covariates/ Strata	Missing Data	Interpretation/ Comments
Proportion of maximum mild, moderate, severe, and any systemic event over Days 1-10 after vaccination (fever, vomiting, diarrhea, fatigue, headache, muscle pain, joint pain, plus any systemic event); also antipyretic/pain medication use	Safety	Fisher exact	Vaccine group	See Section 6.2.3	Assess reactogenicity
Proportions of subjects with the indicated systemic event each day, plus any systemic event	Safety	Descriptive only	Vaccine group	N/A	No statistical test
Proportions of subjects with moderate or severe indicated systemic event on each day	Safety	Descriptive only	Vaccine group	N/A	No statistical test
Duration of systemic event/fever, but not for any systemic event	Safety	Mann-Whitney	Vaccine group	N/A	Assess reactogenicity
Onset of systemic event/any systemic event/fever	Safety	Mann-Whitney	Vaccine group	N/A	Assess reactogenicity
Subjects reporting any severe local reaction and any severe systemic event on the same day	Safety	N/A	Vaccine group	N/A	Listing of Days 1-10, including day of interest
Listing of unresolved reactions still present on the last e-diary day	Safety	N/A	Vaccine group	N/A	
Completing the e-diary each day	Safety	N/A	Vaccine group	N/A	
Completing the e-diary on Days 1-10	Safety	N/A	Vaccine group	N/A	Categories for days completed are 100%, 75%-<100%, 50%-74%, 25%-49%, and <25%
One or more e-diary entries on or after the day of surgery	Safety	N/A	Vaccine group	N/A	
Proportion of subjects with surgery on Days 1, 2, 3, etc, after vaccination	Safety	N/A	Vaccine group	N/A	Days with zero proportions may be omitted; eg, there is no expectation of subjects' receiving surgery on the day

**Table 20. Summary of Analyses for Local Reactions and Systemic Events**

Endpoint	Population	Statistical Method	Model/ Covariates/ Strata	Missing Data	Interpretation/ Comments
					after vaccination
Number needed to harm	Safety	Reciprocal on 95% CI on difference between investigational products	Vaccine group	N/A	Performed for any local reaction and any systemic event

Abbreviations: e-diary = electronic diary; N/A = not applicable.

**8.2.2.4. Concomitant Medications, Vaccinations, and Blood Products**

Analyses for concomitant medications, nonstudy vaccines, and blood products are summarized in Table 21.

**Table 21. Summary of Analyses for Concomitant Medications, Nonstudy Vaccines, and Blood Products**

Endpoint	Population	Statistical Method	Model/ Covariates/ Strata	Missing Data	Interpretation/Comments
Antibiotics, systemic steroids	Safety	Fisher exact	Vaccine group	N/A	3 Time intervals: 1. The day of vaccination to the day before surgery 2. The day of surgery until study completion 3. The day of vaccination until study completion
Intraspinal steroids	Safety	Fisher exact	Vaccine group	N/A	2 Time intervals: 1. From 6 months before enrollment until the day before vaccination 2. The day of vaccination until study completion
Nonstudy vaccines	Safety	Fisher exact	Vaccine group	N/A	2 Time intervals: 1. From 6 months before enrollment until the day before vaccination 2. The day of vaccination until study completion

**Table 21. Summary of Analyses for Concomitant Medications, Nonstudy Vaccines, and Blood Products**

Endpoint	Population	Statistical Method	Model/Covariates/Strata	Missing Data	Interpretation/Comments
Days of antibiotic use	Safety	van Elteren	Vaccine group; site for van Elteren test	N/A	3 Time intervals: 1. The day of vaccination to the day before surgery 2. The day of surgery until study completion 3. The day of vaccination until study completion
Blood products: transfusions (blood product type, origin of blood product if packed RBCs or whole blood, use of cell saver, number of units, number of transfusions per subjects)	Safety	CMH for discrete variables, van Elteren for number of units and number of transfusions	Vaccine group; site for van Elteren test	N/A	3 Time intervals: 1. The day of vaccination until before surgery 2. Days 1-7 (where Day 1 is the day of surgery) 3. Days 8 or more

Abbreviations: CMH = Cochran-Mantel-Haenszel; N/A = not applicable; RBC = red blood cell.

All analyses will be conducted in the safety population. No subgroup analyses are proposed.

